## **6.9. Study Drug Acceptability**

To evaluate the acceptability and palatability of edasalonexent, caregivers will complete the study drug questionnaire listed in [Appendix 4](#) at timepoints indicated in [Appendix 1](#).

## **6.10. Total Volume of Blood Collected**

The total number of venipunctures and the total volume of blood collected during the study will be limited to that needed for safety monitoring, PK, and PD measurement. Refer to the SRM and/or laboratory manual for the collection preparation and procedures as well as the estimated total volume of blood to be collected during the study. The total blood volume collected from each patient for the entire study is within the guidelines set forth by the World Health Organization (WHO) (Howie, 2011).

## 7. ADVERSE EVENTS AND ADVERSE EVENT REPORTING

At each study visit, patients will be evaluated for new AEs and the status of existing AEs. The Investigator may elicit symptoms using an open-ended question, followed by appropriate questions that clarify the patient's verbatim description of AEs or change in concomitant medications. The enrolling Investigator is responsible for safety oversight of data for all visits unless the patient is transferred to another site for all subsequent visits. All AEs from the time of signing the informed consent through follow-up will be recorded on the eCRF.

### 7.1. Timeframe for Collection of Adverse Events

#### 7.1.1. Adverse Events Occurring Prior to Study Treatment

All AEs that occur between the time informed consent is provided and the patient's receipt of the first dose of investigational product will be considered pretreatment AEs.

#### 7.1.2. Adverse Events Occurring After Study Treatment

All AEs that occur from the time of the administration of the first dose of investigational product through the end of the safety follow-up will be considered treatment-emergent AEs (TEAEs).

#### 7.1.3. Adverse Events Occurring Following Patient Discontinuation of Treatment

For patients who prematurely discontinue study treatment (see [Section 5.2.5](#)), but who are not withdrawn from the study, AEs will continue to be recorded until the patient completes the study (see [Section 3.3.3.1](#) for definition of patient completion). See [Section 7.6](#) for reporting requirements after the patient completes the study.

## 7.2. Definitions

### 7.2.1. Definition of an Adverse Event

An AE is any untoward medical occurrence in a clinical investigation patient, which does not necessarily have a causal relationship with the investigational product (active or placebo drug, biologic, or device). An AE can, therefore, be any unfavorable and unintended symptom, sign, disease or condition, or test abnormality, whether considered related to the investigational product.

Adverse events include:

- Symptoms described by the patient or signs observed by the Investigator or medical staff
- Test abnormalities (laboratory tests, ECG, X-rays, etc.) that result in an alteration in medical care (diagnostic or therapeutic)

Adverse events do not include:

- Changes that are characteristic of disease progression in Duchenne

Abnormalities present at Baseline are considered AEs only if they reoccur after resolution or they worsen during the study.

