#### **6.4.3. Clinical Laboratory Tests**

Blood and urine samples will be collected for clinical laboratory evaluations (see [Appendix 3](#) for a complete list of analytes).

The clinical laboratory tests to be done at Screening include hematology with differential, chemistry, and urinalysis.

Blood samples for ACTH and cortisol will be obtained at Baseline before initiation of treatment.

Chemistry, hematology, and ACTH/cortisol assessments done during the treatment period will be performed in the morning when possible.

A central laboratory will provide collection supplies, arrange collection, and perform analysis of clinical laboratory evaluations indicated in [Appendix 3](#). Using the central laboratory for unscheduled clinical laboratory evaluations and repeat testing is recommended. Procedures for the handling and shipment of all central laboratory samples will be included in the Laboratory Manual. Specimens will be appropriately processed by the central laboratory facility and laboratory reports will be made available to the Investigator in a timely manner to ensure appropriate clinical review.

The enrolling Investigator is responsible for reviewing and signing all laboratory reports unless the patient is transferred to another site for all subsequent visits. The clinical significance of each value outside of reference range will be assessed by the Investigator and documented as either not clinically significant (NCS) or clinically significant. All clinically significant values require a comment and the out-of-range value or the overlying diagnosis (or value if the diagnosis is unknown) must be captured as an AE.

Clinical laboratory reports will serve as source documents.

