### 7.2.2. Definition of a Serious Adverse Event

Seriousness of an AE serves as a guide for defining regulatory reporting obligations. An SAE is any AE that results in any of the following:

Death: The patient died as the result of the event.

Life-threatening event: Any AE that places the patient, in the view of the Investigator, at immediate risk of death from the AE as it occurred, i.e., does not include an AE that had it occurred in a more severe form, might have caused death.

Required or prolonged inpatient hospitalization: The AE resulted in an initial inpatient hospitalization or prolonged an existing hospitalization of the patient. Note: Planned hospital admissions, or surgical procedures for an illness or disease that existed before the administration of the study treatment or before the patient was enrolled in the study, will not be captured as SAEs unless they occur at a time other than the planned date.

Persistent or significant disability/incapacity: An AE that results in a substantial disruption of a person's ability to conduct normal life functions.

Congenital anomaly/birth defect: A congenital anomaly/birth defect that occurs in the offspring of a patient exposed to the investigational product.

Important medical events: An AE that may not result in death, be life-threatening, or require hospitalization may be considered an SAE when, based upon appropriate medical judgment, the event may jeopardize the patient or subject and may require medical or surgical intervention to prevent one of the outcomes listed above.

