## 7.3. Evaluation of Adverse Events/Serious Adverse Events

### 7.3.1. Relationship to Study Treatment

Assessment of the association between the AE and study drug exposure is important for regulatory reporting. For each AE/SAE, the Investigator will determine whether there is a reasonable possibility that the AE may have been caused by the study drug according to the following categories:

Not Related: The AE is clearly not related to study drug.

Unlikely Related: There is no evidence of a causal relationship between study drug and the AE; although such relationship cannot be ruled out.

Possibly Related: There is some evidence supporting the possibility of a causal relationship between study drug and the AE.

Related: There is strong evidence that there is a causal relationship between study drug and the AE.

A relationship to the investigational product must be given for each AE/SAE recorded, even if there is only limited information at the time. The Investigator may change his/her opinion of causality in light of follow-up information, amending the AE/SAE report accordingly.

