#### 7.6. Reporting of Serious Adverse Events

All SAEs occurring from the time of informed consent until 30 days following the last administration of study drug must be reported within 24 hours of the knowledge of the occurrence (this refers to any AE that meets any of the aforementioned serious criteria in [Section 7.2.2](#)). SAEs that the Investigator considers related to study drug that occur after the 30-Day follow-up period must also be reported.

All SAEs should be reported immediately within 24 hours of site awareness of the event. The Investigator should complete the paper study SAE report form and send the initial SAE report within 24 hours to PV department via email/fax as per contact details below.

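### The adverse-event definition excludes characteristic Duchenne progression without excepting fatal, life-threatening or hospitalised events (a narrow, minor gap)

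*Protocol*

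**What the plan says.** Protocol 7.2.1 defines an AE broadly, without regard to cause, and then takes one class of event out: "Changes that are characteristic of disease progression in Duchenne". No qualifier about seriousness follows. The next sentence deals with findings already there at entry: "Abnormalities present at Baseline are considered AEs only if they reoccur after resolution or they worsen during the study".

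Three later sections build on that definition:

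- Section 7.2.2: "An SAE is any AE that results in any of the following", followed by the usual serious criteria.
- Section 7.6, on what must be reported within 24 hours: "this refers to any AE that meets any of the aforementioned serious criteria".
- Section 7.3.1: "A relationship to the investigational product must be given for each AE/SAE recorded".

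Section 7.2.2 also has a note on pre-existing disease. "Planned hospital admissions, or surgical procedures for an illness or disease that existed before the administration of the study treatment", or before enrolment, are not captured as SAEs unless they happen at a time other than the one planned.

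**The concern.** Leaving expected decline out of the AE tables is sensible when function is the efficacy outcome. The difficulty is that the exclusion acts before anything is recorded. A site that decides an event is progression has, in effect, already made a causality judgement, and no rating or report need exist for anyone else to look at. For slow functional decline that matters little, because the efficacy tests record it. For a death, a life-threatening event or an unplanned admission it matters more: those are the events for which a prompt report and an explicit causality opinion are wanted whatever the presumed cause, above all in a placebo-controlled trial in young children. Sites may also differ in how they read the rule, since 7.2.1 does not say how the exclusion ranks against the other recording rules.

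**Working it through.** No arithmetic applies. The check is to follow an event through the text and see whether any rule brings it back.

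**Step 1: does the exclusion carry through?** Section 7.2.2 makes every SAE an AE first. Section 7.6 limits expedited reporting to AEs that meet a serious criterion. Section 7.3.1 asks for causality only for events recorded as AEs or SAEs. An event removed in 7.2.1 therefore drops out of all three. SAP 4.13.1, on adverse-event analysis, does not restore it.

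**Step 2: which other rules could catch it?**

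- *Laboratory values (6.4.3).* For a clinically significant value, either the out-of-range result or "the overlying diagnosis (or value if the diagnosis is unknown) must be captured as an AE". This works only if there is such a value.
- *New treatment (6.4.5).* The indication for any new drug or therapy is recorded as an AE. This is probably the widest net, but it needs a new treatment.
- *Test abnormalities (7.2.1).* These are AEs if they change diagnostic or therapeutic care.
- *Procedures (7.4).* The condition behind a procedure is recorded. This needs a procedure.
- *Abnormal safety assessments (7.4).* These count only if they meet the definition in 7.2, so the rule leads back to the exclusion.
- *Death (7.4).* Death itself is reported as an AE when the AE leading to it is not known. Whether this covers a death put down to progression is open: one site may say that no causal AE is known, so the rule applies; another may say that the cause is known.
- *Worsening from Baseline (7.2.1).* The wording is "only if", which is a necessary condition. Read as sufficient, it would collide with the exclusion, since Duchenne progression is largely worsening of what was present at Baseline.

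None of these rules mentions the exclusion, and none says which prevails.

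**Step 3: is anything left?** Section 2 of the protocol includes frequent falls in its picture of boys by 8 years of age. Boys may enter at any age below 8.0 and are treated for 52 weeks, so some pass 8 on study. Take a boy admitted overnight for observation after a fall put down to weakness. No injury is found, nothing new is prescribed, no procedure is done and no test result alters care. The admission meets the hospitalisation criterion, yet every rule in Step 2 can be read as not applying. A site that regards the fall as characteristic of the disease could record nothing. The admission would also be invisible in the efficacy data if function was unchanged.

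**Step 4: what does the planned-admission note imply?** It removes planned admissions for pre-existing disease and by implication leaves unplanned ones in. That suggests the authors wanted unplanned admissions reported. But the note sits inside a definition that still begins with an AE, so it does not override 7.2.1.

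**The case against.** The strongest reply is that the example is contrived. The exclusion speaks of changes characteristic of progression. An acute fall with an unplanned admission is more naturally an untoward occurrence, and signs and symptoms are AEs under the same section. Most sites would report it. The entry criteria aim to keep out boys at high risk of imminent loss of ambulation (3.4), the investigator, Medical Monitor and sponsor monitor safety continuously (5.2.3), and the DSMB reviews whatever its charter defines as relevant. SAP Table 1 also has a continuously assessed row that includes change in function, although the protocol's own schedule does not. All of this stands. It makes the gap small, but none of it supplies the missing exception.

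Three stronger readings are tempting, and the documents do not support them.

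- *A reader might infer that disabling loss of function is being hidden and should be an SAE.* It is measured at Weeks 13, 26, 39 and 52, scored as zero speed for the worst timed-test grades (SAP 2.6.2), and compared by arm for each of the 17 NSAA items (SAP 4.10.7). Section 2 says most boys are losing the ability to rise from the floor and climb stairs by 8. Making each such loss a 24-hour SAE would turn the expected efficacy outcome into expedited safety reports.
- *A reader might infer that the wait from a functional visit to the unblinded analysis measures the harm.* It does not. That analysis compares arms, whereas an SAE report concerns one blinded patient. By-arm SAE tables also wait for database lock, unless the DSMB sees them earlier under a charter that is not among the documents.
- *A reader might infer that the exclusion biases the safety comparison.* It applies equally to both arms under blinding, and nothing in the documents shows that edasalonexent produces effects resembling progression.

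**Conclusion.** The point holds in a limited form. As written, 7.2.1 lets a fatal, life-threatening or hospitalised event be left unrecorded if a site attributes it to progression and no other rule catches it. Sections 7.2.2, 7.3.1 and 7.6 then require neither an SAE report nor a causality rating.

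The size cannot be computed. The documents give no rate for such events, and the number may be zero. Efficacy inference is unaffected. I rate it minor: a drafting gap with a patient-safety consequence, worth closing because it is cheap to close.

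The conclusion assumes that no document outside those supplied, such as the Study Reference Manual or the DSMB charter, already instructs sites to report these events.

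**What to change.** Add one sentence to 7.2.1, directly after the exclusion:

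> This exclusion does not apply to any event that is fatal, life-threatening or requires unplanned inpatient hospitalisation, or to any decline the Investigator suspects is related to study drug or considers atypical for Duchenne; these are recorded and, if serious, reported as SAEs with a causality rating, regardless of attribution to DMD.

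Keep expected functional decline captured by the NSAA and timed tests outside the AE definition, even when it is disabling. Leave the planned-admission note in 7.2.2 as it is. Because the later sections all start from the AE definition, no other section needs rewording.

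The cost is one sentence of protocol text, a note to sites, and some additional background-disease SAE entries in both arms. These are probably few, though the documents give no rate from which to estimate them. If the change is made late (Appendix 2 states that every enrolled boy had completed at least Week 26 when the pandemic began), sites would also need one look-back, limited to serious events.

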### 7.2.2. Definition of a Serious Adverse Event

Seriousness of an AE serves as a guide for defining regulatory reporting obligations. An SAE is any AE that results in any of the following:

Death: The patient died as the result of the event.

Life-threatening event: Any AE that places the patient, in the view of the Investigator, at immediate risk of death from the AE as it occurred, i.e., does not include an AE that had it occurred in a more severe form, might have caused death.

Required or prolonged inpatient hospitalization: The AE resulted in an initial inpatient hospitalization or prolonged an existing hospitalization of the patient. Note: Planned hospital admissions, or surgical procedures for an illness or disease that existed before the administration of the study treatment or before the patient was enrolled in the study, will not be captured as SAEs unless they occur at a time other than the planned date.

Persistent or significant disability/incapacity: An AE that results in a substantial disruption of a person's ability to conduct normal life functions.

Congenital anomaly/birth defect: A congenital anomaly/birth defect that occurs in the offspring of a patient exposed to the investigational product.

Important medical events: An AE that may not result in death, be life-threatening, or require hospitalization may be considered an SAE when, based upon appropriate medical judgment, the event may jeopardize the patient or subject and may require medical or surgical intervention to prevent one of the outcomes listed above.

## 7.3. Evaluation of Adverse Events/Serious Adverse Events

### 7.3.1. Relationship to Study Treatment

Assessment of the association between the AE and study drug exposure is important for regulatory reporting. For each AE/SAE, the Investigator will determine whether there is a reasonable possibility that the AE may have been caused by the study drug according to the following categories:

Not Related: The AE is clearly not related to study drug.

Unlikely Related: There is no evidence of a causal relationship between study drug and the AE; although such relationship cannot be ruled out.

Possibly Related: There is some evidence supporting the possibility of a causal relationship between study drug and the AE.

Related: There is strong evidence that there is a causal relationship between study drug and the AE.

A relationship to the investigational product must be given for each AE/SAE recorded, even if there is only limited information at the time. The Investigator may change his/her opinion of causality in light of follow-up information, amending the AE/SAE report accordingly.

### 7.3.2. Severity Grading of Adverse Event Scoring

Note that severity is not the same as "seriousness," which is defined in [Section 7.2.2](#).

The Investigator will grade the severity of all AEs/SAEs as mild, moderate, or severe, based on the following definitions (developed from Clinical Data Interchange Standards Consortium [CDISC] Study Data Tabulation Model [SDTM] standard terminology v3.1.1):

Mild: An AE that is usually transient and may require only minimal treatment or therapeutic intervention. The event does not generally interfere with usual activities of daily living.

Moderate: An AE that is usually alleviated with specific therapeutic intervention. The event interferes with usual activities of daily living, causing discomfort, but poses no significant or permanent risk of harm to the research participant.

Severe: An AE that interrupts usual activities of daily living, or significantly affects clinical status, or may require intensive therapeutic intervention.

### **7.3.3. Outcome**

Outcome describes the status of the AE. The Investigator will provide information regarding the patient outcome of each AE.

Possible results of an AE outcome are defined as follows:

Fatal: The termination of life as a result of an AE.

Not recovered/not resolved: The patient has not recuperated or the AE has not improved.

Recovering/resolving: The patient is recuperating or the AE is improving.

Recovered/resolved: The patient has recuperated or the AE has resolved.

Recovered with sequelae/resolved with sequelae: The AE has resolved, but the patient has been left with symptoms or pathology.

Unknown: Not known, not observed, not recorded, or refused.

### **7.3.4. Action Taken Regarding the Investigational Product**

The Investigator will be required to provide the action taken regarding investigational product (e.g., active, comparator) in response to the AE according to the following categories:

Dose not changed: No change in administration of the investigational product.

Dose reduced: Reduction in the frequency, strength or amount of investigational product administered.

Drug (investigational product) interrupted: Temporary interruption (termination) in administration of the investigational product.

Drug (investigational product) withdrawn: Administration of the investigational product terminated (no further dosing).

Not applicable: Determination of a value is not relevant in the current context.

Unknown: Not known, not observed, not recorded, or refused.

#### 7.4. Recording of Adverse Events/Serious Adverse Events

All AEs/SAEs experienced by the patient will be recorded on the eCRF. The following information will be recorded: a concise description of the event; date and time of event onset and resolution; determination of seriousness, severity, corrective treatment, outcome, and relationship to investigational product; and, action taken regarding the investigational product. Abnormal vital signs, laboratory results, or other abnormal safety assessments noted in [Section 6.4](#) will be recorded as an AE if they meet the definition of an AE (see [Section 7.2](#)). When possible, a diagnosis should be recorded as an AE rather than symptoms or isolated laboratory abnormalities related to that diagnosis. A medical or surgical procedure is not an AE; rather the condition leading to the procedure should be recorded as the AE. If the condition is not known, the procedure must be reported as an AE instead. Similarly, death is not an AE, but rather is the outcome of the AE(s) that resulted in death. If the AE(s) leading to death are not known, then death must be reported as an AE.

All SAEs experienced by the patient will be recorded on the AE eCRF and reported to the Sponsor or its designee according to [Section 7.6](#).

#### 7.5. COVID-19 Adverse Events and/or Serious Adverse Events

For any study participants exhibiting symptoms consistent with COVID-19, these need to be captured as adverse events or serious adverse events according to the established safety reporting system specified in the study protocol. In the event a participant tests positive for COVID-19, or if no testing is available, ensure appropriate documentation of the AE and/or SAE of COVID-19 is reflected in the eCRF and the study specific SAE report form.

